3 STUDY OBJECTIVES

We plan a feasibility exploratory study among survivors of critical illness to investigate whether CPET and wearable accelerometry can be used during early post-intensive care recovery.

We aim to explore the relationship between in-hospital factors, anaemia management strategy, and critical illness survivors' functional capacity, their activity of daily living, fatigue, and quality of sleep by recruiting a cohort of patients participating in a randomised trial of two strategies for managing anaemia following ICU discharge (the ABC post ICU study).

As further comparative cohorts, and to gain an understanding of functional capacity following an ICU admission, we will collect functional data on two additional cohorts: first, patients who received 24 hours or more of mechanical ventilation in the ICU, were discharged alive, but were not eligible for the ABC post ICU study due to lack of anaemia; second, patients who required level 2 care (HDU care) for at least 24 hours (no mechanical ventilation)

3.1 OBJECTIVES

- To provide objective figures regarding the functional capacity of critical illness survivors close to the point of hospital discharge.
 - o Cardiopulmonary exercise test (cycle-ergometer based)
- To measure patient-reported levels of fatigue during the immediate post ICU discharge period
 - Visual Analogue Scale Fatigue (VAS-F)
- To measure patient-reported performance in the daily living activities
 - Barthel Index (BI)
- To access day (daytime activity) and night movement (sleep patterns) of intensive care survivors for two months since enrollment
 - Wearable wrist-worn accelerometer (Geneactiv device)
- To explore the relationship between these variables and anaemia status following ICU discharge
- To compare several different cohorts of patients discharged from critical care in terms
 of:
 - o Fatigue levels (VAS-F)
 - Activity of daily living (BI)
 - o Physical activity and quality of sleep (accelerometery)
 - o Cardiopulmonary exercise capacity (CPET)

3.2 ENDPOINTS

3.2.1 Feasibility endpoints

- Proportion of patients approached who agree to participate in the sub-study
- Proportion of patients who agree to take part, who are able to attempt the CPET test
- Proportion of patients who agree to take part and completed an average duration of useable accelerometer recordings
- Safety and adverse events related to the CPET and wrist actigraphy device

3.2.2.2 Secondary endpoints

- The effect of haemoglobin concentration on daily activity, sleep quality, cardiopulmonary performance and feeling of fatigue
- Causes of exercise limitation among critical illness survivors
- Possible links between ICU related factors and patient's cardiopulmonary exercise capacity, fatigue, quality of sleep and daily activity
- Possible associations between both exercise capacity (peak oxygen consumption) and daily physical activity (step count, activity counts per day, time spent in activity) with a hospital readmission rate

4 STUDY DESIGN

A prospective exploratory single-centre study, conducted in conjunction with a large multi-centre randomised controlled trial.

All eligible patients successfully discharged alive from the general ICU/HDU within the Edinburgh Royal Infirmary and Western General Hospital will be approached at the post-ICU/HDU wards and asked for consent to take part in the study.

4.1 Groups

We plan to recruit four different cohorts of patients:

Group one (feasibility group): 'ICU survivors'

These patients should have received level 3 care and ventilatory support for more than 24 hours in the ICU, and should not be involved in the ABC post-ICU trial. Patients who have contraindications for blood transfusion or rejected a blood transfusion if indicated might be included. Patients already involved in the other studies can be co-enrolled if the principal investigator agrees.

Group two: 'Anaemic ICU survivors - usual care (restrictive) transfusion strategy'

These patients will have consented to participate in the ABC-post ICU trial, and randomised to the restrictive strategy (transfused at a lower haemoglobin threshold).

Group three: 'Anaemic ICU survivors - liberal transfusion strategy

These patients will have consented to participate in the ABC-post ICU trial, and randomised to the liberal strategy (transfused at a higher haemoglobin threshold).

Group four: Patients who required high dependency care (Level 2 care) in the critical care unit

Participants in this group should have been treated for at least 24 hours at either ICU or HDU level, but required only level 2 care (no mechanical ventilation in the ICU or HDU; requirement for only single organ support).

4.2 Overview of proposed assessments and measurements.

Following the enrolment on the same day, all participants will be asked to complete short self-reported questionnaires about their ability to undertake activities of daily living (Barthel Index) and self-reported feelings of fatigue (VAS-F scale). Later, close to the point of hospital discharge or on the day of the cardiopulmonary test both questionnaires will be administered one more time.

In addition, on the day of enrolment, all participants will be asked to put on and wear an accelerometer device on their non-dominant wrist for up to 2 months, which is the usual time when the GENEActive accelerometer requires to be charged. Participants are encouraged to wear it for as long as possible, but taking it off is not prohibited. In the unlikely event that patients experience hypersensitivity or allergy to the device strap, they will be advised to stop wearing the strap and seek medical help by contacting medical services (either through their GP, emergency department or ambulance service).

Finally, for those participants who agreed to undergo the cardiopulmonary exercise test (CPET), the test will be arranged, which might happen in the interval of 5 to 20 days post ICU discharge. The CPET will take place in the hospital cardiopulmonary exercise testing laboratory and comprises a maximal, symptom-limited incremental exertion test on a cycle ergometer. All tests will be carried out according to an incremental protocol, where the increment rate of pedal resistance is calculated individually, allowing to achieve maximal exertion within 8-12 minutes, which has been shown to elicit optimal results. For more details regarding the cardiopulmonary exercise test, please see the appendix. Despite applied measures to increase the CPET completion rate among participants such as at the screening and enrollment stages, excluding patients with orthopaedic/neurologic pathology along with those who have contraindications to be tested and close collaboration with the cardiopulmonary exercise testing team, respectively, some participants might not be able to undertake or complete the test. These could be due to various individual or organizational reasons. In such cases, we will try to reschedule the exercise test and regardless of the presence or absence of the CPET result, participants will not be subjected to exclusion from the study.

Schematically the study flow is illustrated in figure 1 below.

[figure not shown]

Figure 1. Study flow

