1.3 Anaemia and its current management in critical care patients

In accordance with the World Health Organization (WHO): "Anaemia is a condition in which the number of red blood cells or the haemoglobin concentration within them is lower than normal. Haemoglobin is needed to carry oxygen and if you have too few or abnormal red blood cells or not enough haemoglobin, there will be a decreased capacity of the blood to carry oxygen to the body's tissues. This results in symptoms such as fatigue, weakness, dizziness and shortness of breath, among others. The optimal haemoglobin concentration needed to meet physiologic needs varies by age, sex, the elevation of residence, smoking habits and pregnancy status" (available at https://www.who.int/health-topics/anaemia#tab=tab_1). Generally, this happens during and after a decrease in the circulating red blood cell volume together with haemoglobin concentration and can occur for various reasons. According to a plethora of studies, anaemia is one of the most frequent complications of critical illness and can persist in those who survive the critical phase.

In general terms, anaemia is caused by three types of abnormalities: Impaired red blood cell production; increased destruction of red blood cells; and blood loss. All the reasons listed above might be present and coincide with a critically ill individual. It has been estimated that during the course of critical illness during ICU stay haemoglobin (Hb) concentration decreases on average by 0.52 +/- 0.69 g/dL/day in non-bleeding patients, with a maximum rate during the first 3 days, then slowly but steadily afterwards (Nguyen et al. 2003). Anaemia prevalence among critically ill patients experiencing prolonged ICU stay is up to 97-100% and as a consequence, 75-97% of ICU survivors have various degrees of anaemia at ICU or hospital discharge (Walsh et al. 2006); (Shah et al. 2016); In addition, normal physiological responses to anaemia are impaired, and the body responds poorly to erythrogenesis stimulating agents, such as erythropoietin. This is probably due to bone marrow suppression mediated by an ongoing inflammatory process, including through the key regulating hepcidin pathway (Loftus et al. 2018). Nonetheless, at present, only around 19% of anaemic patients receive RBC transfusion post ICU on general wards to correct anaemia (Shah et al. 2016).

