Modern accelerometers can provide RAW acceleration data that widens the analytical possibilities. Most acceleration data analysis algorithms have been based on data obtained from healthy volunteers, hence raising the concern about their validity among populations with underlying diseases (Tsanas, Woodward, and Ehlers 2020), (Conley et al. 2019). Therefore, more studies are still required that will aid this method, along with developing and tailoring disease-specific analytic algorithms, including validation against other mobility scales.

Key advantages of the accelerometery are unobtrusiveness compared to other methods used to access physical activity, like direct observation or video monitoring and the possibility to collect activity data for a long period. Further, recorded data can describe both physical activities and sleep patterns during everyday living by applying custom analytical approaches. The development in data science enabled the detection of activity of daily living, solely from the accelerometer recordings. These make this method relevant to use in patients recovering from critical illness and have the potential to detect a difference in physical recovery trajectories between patients subjected to interventions aimed at improving functional capacity, either directly or indirectly, such as anaemia treatment with blood transfusion.

2 ABC Post ICU Trial

The UK's large multicenter ABC post-ICU clinical trial will explore the impact of the post ICU blood transfusion strategy on clinical outcomes among anaemic ICU survivors. The main aim of this trial is to determine whether a higher blood haemoglobin level achieved with RBC transfusion in the post ICU setting is beneficial in terms of symptoms of fatigue, functional status, activities of daily living, and overall quality of life compared to 'usual care' restrictive transfusion practice.

Trial's Inclusion criteria:

- Patient who required level 3 ICU care at any time point during the current hospital admission (defined as advanced respiratory support and/or at least two organ support)
- · Patient considered ready for discharge from the ICU by the caring clinical team
- Hb≤94g/L when ready for ICU discharge or during the first seven days following the decision by the treating clinician that the patient is **fit for** ICU discharge
- Age ≥16 years.
- Consent provided (by a participant or in accordance with appropriate mental capacity legislation for the site)

Exclusion criteria:

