- Contraindication or objection to RBC transfusion
- · Active bleeding when screened
- Primary neurological ICU admission diagnosis
- Patients discharged from the ICU following cardiac surgery
- · Currently receiving or planned to receive end-of-life care
- Not expected by the clinical team to survive to hospital discharge.
- Patient with a proven chronic haematological disease that requires regular RBC transfusion to treat anaemia
- Patient with dialysis-dependent chronic renal failure prior to ICU admission
- Patient receiving regular erythropoietin (or erythropoiesis-stimulating agents) treatment for anaemia prior to ICU admission.
- Unable to obtain consent (from a patient or in accordance with appropriate mental capacity legislation for the site)

All eligible participants will be subject to computer-based randomisation and centre block allocation with a 1:1 ratio into a comparator and intervention groups. It is assumed that the only difference between groups will be in-hospital anaemia management. Patients in the comparator group will be treated according to current NICE guidance (see: www.nice.org.uk/guidance/ng24/chapter/Recommendations#red-blood-cells-2) which recommends haemoglobin concentration less than 70g/L as a blood transfusion trigger and a target haemoglobin concentration between 70-90g/L while patients in the intervention group will have higher blood transfusion trigger and target concentration less than 100g/L and 100-120g/L, respectively. It ought to be remarked that patients in the intervention group will at least receive a transfusion of one RBC unit following randomisation.

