5.2 INCLUSION CRITERIA (All groups)

- Patient older than 16 years.
- Patient who required either level 2 or 3 ICU care at any time point during the current hospital admission (defined as requiring support for a single failing organ system and advanced respiratory support and/or at least two organ support, respectively)
- Patients who required either level 2 or 3 care for at least 24 hours
- Patient with the mental capacity to give consent for the study

Group one:

- Critical illness survivors who have been on mechanical ventilation for more than 24 hours
- Not involved in the post-ICU ABC trial and might have a contraindication or objection to blood transfusion

Group two:

• Patient enrolled in the restrictive transfusion strategy group of ABC post ICU trial (Haemoglobin concentration at ICU discharge of >94g/L)

Group three:

 Patient enrolled in the liberal transfusion strategy group of the ABC post ICU study (Haemoglobin concentration at ICU discharge of >94g/L)

Group four

 Critical illness survivors who have not been mechanically ventilated in the ICU or HDU, and received level 2/HDU care for at least 24 hours

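### Section 3 describes group one as lacking anaemia, but its entry criteria set no haemoglobin limit, so it cannot be read as a non-anaemic comparator

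*Protocol*

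**What the plan says.** Section 3 announces two further comparative cohorts. The first is survivors ventilated for 24 hours or longer who left the ICU alive, "but were not eligible for the ABC post ICU study due to lack of anaemia". Of the four groups in section 4.1, only group one matches that description.

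The operative criteria read differently. Section 4.1 opens group one with "These patients should have received level 3 care and ventilatory support for more than 24 hours in the ICU", requires that the patient is not in ABC, and then states: "Patients who have contraindications for blood transfusion or rejected a blood transfusion if indicated might be included". Section 5.2 asks for ventilation beyond 24 hours and "Not involved in the post-ICU ABC trial and might have a contraindication or objection to blood transfusion". Neither section gives group one a haemoglobin limit, and the lists that apply to all groups in 5.2 and 5.3 contain none.

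Section 2 gives the ABC criteria. Eligibility needs "Hb≤94g/L when ready for ICU discharge or during the first seven days following the decision by the treating clinician" (of fitness for ICU discharge), and one of the exclusions is "Contraindication or objection to RBC transfusion".

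**The concern.** Section 3 makes absence of anaemia the reason a patient is in this cohort. Sections 4.1 and 5.2 replace that reason with absence from ABC, which is a different thing. A patient can be outside ABC and still be below its haemoglobin threshold.

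The protocol lists a relationship with anaemia status and a comparison of cohorts among its objectives (3.1). It labels groups two and three as anaemic (4.1) and plans between-group tests (10.2). A reader who takes section 3 at its word will read a difference between group one and group two as a difference between non-anaemic and anaemic survivors. The criteria do not guarantee that. With a target of 10 per group (5.1), each anaemic patient in group one is 10% of the comparator.

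**Working it through.** **1. The plan's own figures.** The protocol states no anaemic share for group one, no effect size and no power. Its one calculation is recruitment (10.1): 2 per month × 18 months = 36, against a stated 35-40. Half of 35-40 is 17.5-20, and adding 20 for the other two groups gives 37.5-40, against a stated 40. This point does not affect that target.

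**2. Who can enter group one below the ABC threshold.**
- Patients with a contraindication or objection to transfusion. ABC excludes them whatever their haemoglobin (section 2); group one admits them (4.1, 5.2).
- Patients who rejected a transfusion that was indicated (4.1 only). Section 1.3 puts usual practice at transfusing below 70-80 g/L, so these patients would typically lie under 94 g/L.
- Patients eligible for ABC who declined it. No group one criterion keeps them out.

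**3. Group one versus group two.** Let p be the share of group one with Hb ≤94 g/L. Let μN be the mean outcome of its other members, μA the mean of the anaemic members, and μ2 the group two mean. Then

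group one − group two = (1 − p)(μN − μ2) + p(μA − μ2).

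If the anaemic members resemble group two (μA = μ2), the second term vanishes and a fraction 1 − p remains:

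| Assumed p | Patients out of 10 | Share of the difference kept |
|---|---|---|
| 20% | 2 | 80% |
| 30% | 3 | 70% |
| 50% | 5 | 50% |

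**4. Group one versus group three.** With group three mean μ3,

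group one − group three = (μN − μ3) + p(μA − μN).

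Section 2 gives group three a target of 100-120 g/L and at least one unit after randomisation, so the sign of μN − μ3 is unknown. If anaemia worsens the outcome, the second term lowers the group one mean. That shrinks or reverses the difference if μN > μ3, and widens it if μN < μ3.

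**5. Practical scale, for illustration.** Assume a 25 g/L haemoglobin gap. Section 2 reports about 1% of VO2max per 3 g/L (in healthy athletes). Table 1 in section 1.8 gives a peak VO2 of 13.6 (SD 3.9) ml/kg/min for one control group at baseline. The difference is 13.6 × (25/3)/100 = 1.13 ml/kg/min. With 10 per group and two-sided 0.05, the normal approximation gives power Φ(δ/(3.9√(2/10)) − 1.96), counting rejections in the true direction:
- p = 0: δ = 1.13, power 9.5%
- p = 30%: δ = 0.79, power 6.6%

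For gaps of 15 and 35 g/L, power at p = 0 is 5.8% and 14.7%; at p = 30% it is 4.6% and 9.3%.

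**The case against.** The strongest reply is that group one was never firmly cast as a non-anaemic control. That role rests on one clause in section 3, whose stated purpose is broader: to learn about functional capacity after an ICU admission. Section 4.1 calls group one the feasibility group, and the transfusion exception appears in both 4.1 and 5.2, which suggests intent. Haemoglobin is collected at baseline (8.1), its effect is a secondary endpoint (3.2.2.2), and regression is planned (10.2). None of that depends on the group label. The study is exploratory and unpowered, and the illustration above shows a between-group test on these inputs would have little power in any case.

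Most of this stands, and it limits the weight of the point. It does not reconcile section 3 with 4.1 and 5.2. If the exception is intended, section 3 is wrong.

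A reader might also infer more than the documents support:
- **That every anaemia contrast is biased towards zero.** Step 4 shows this does not follow for group three, nor for groups two and three pooled.
- **That p must be large because** "75-97% of ICU survivors have various degrees of anaemia at ICU or hospital discharge" **(section 1.3).** That range covers any degree of anaemia, not Hb ≤94 g/L, and group one already excludes the patients who joined ABC. It does not supply p.
- **That both sections admit patients with an indicated transfusion.** Only 4.1 says so, and only for rejection. The wording in 5.2 could describe a patient who is not anaemic.
- **That group one is how the study separates anaemia from critical illness.** The protocol does not say this.

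**Conclusion.** The contradiction is real. As written, the criteria can fill group one with patients who are outside ABC for reasons other than lack of anaemia, so it cannot be reported as a non-anaemic cohort.

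The consequence is confined to interpreting group-level comparisons that involve group one. The figures of 80%, 70% and 50% apply only to the contrast with group two, at assumed shares, and only if the anaemic members resemble group two. If they do worse than group two, less of the difference is kept. The randomised comparison of groups two and three, the feasibility endpoints and analyses on measured haemoglobin are untouched. This should be fixed, but it does not undermine the study.

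**What to change.** Reconcile the sections in one of two ways.

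(a) Add to group one in 4.1 and 5.2 that the patient did not meet the ABC haemoglobin criterion (Hb ≤94 g/L when ready for ICU discharge or in the following 7 days, or up to enrolment if that is earlier). Report patients with a transfusion contraindication or refusal who do meet it as a separate descriptive stratum, outside any anaemia contrast.

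(b) Remove the lack-of-anaemia clause from section 3. State that anaemia contrasts will classify participants by measured haemoglobin and not by group label.

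In either case, also reconcile 5.2, which gives groups two and three an ICU-discharge haemoglobin above 94 g/L, with the ABC criterion of 94 g/L or lower in section 2. Otherwise the anaemia boundary stays contradictory on the other side of the contrast.

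The cost is a short wording change that uses haemoglobin values already in the record. Option (a) may slow group one recruitment slightly; option (b) adds a little analysis work. Neither touches a transfusion rule.

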5 STUDY POPULATION

Adult patients treated for at least 24 hours in the critical care unit within the Royal Infirmary Edinburgh or Western General Hospital and successfully discharged are potentially eligible for the study.

5.1 NUMBER OF PARTICIPANTS

This is a feasibility study. Target recruitment was set at 40 subjects, divided into four groups. The aim will be to recruit 10 patients to each of the patient groups. If recruitment to some groups is slow or unlikely to reach the target of 10 patients, we will increase recruitment to the other groups to achieve a total sample size of 40 patients, given the feasibility design.

5.2 INCLUSION CRITERIA (All groups)

- Patient older than 16 years.
- Patient who required either level 2 or 3 ICU care at any time point during the current hospital admission (defined as requiring support for a single failing organ system and advanced respiratory support and/or at least two organ support, respectively)
- Patients who required either level 2 or 3 care for at least 24 hours
- Patient with the mental capacity to give consent for the study

Group one:

- Critical illness survivors who have been on mechanical ventilation for more than 24 hours
- Not involved in the post-ICU ABC trial and might have a contraindication or objection to blood transfusion

Group two:

• Patient enrolled in the restrictive transfusion strategy group of ABC post ICU trial (Haemoglobin concentration at ICU discharge of >94g/L)

Group three:

 Patient enrolled in the liberal transfusion strategy group of the ABC post ICU study (Haemoglobin concentration at ICU discharge of >94g/L)

Group four

 Critical illness survivors who have not been mechanically ventilated in the ICU or HDU, and received level 2/HDU care for at least 24 hours

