10 STATISTICS AND DATA ANALYSIS

10.1 SAMPLE SIZE CALCULATION

The study is an exploratory study associated with the ABC post-ICU trial. The estimated recruitment to the ABC post-ICU trial at the Edinburgh Royal Infirmary is 2 patients per month. The trial aims to recruit for at least 18 months but is likely to be prolonged by the impact of the COVID pandemic. Total recruitment is likely to be 35-40 patients within groups 2 and 3 of this study. Assuming around 50% of patients agree to participate in this additional study, a feasible recruitment target is 20 patients (10 from each randomisation group). We will aim to recruit up to 20 patients in the other two groups over the same period. The total target sample size will be 40 patients.

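### Section 5.2 gives groups two and three a haemoglobin above 94 g/L at ICU discharge, the reverse of the ABC trial's entry rule for the same patients

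*Protocol*

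**What the plan says.** Under the inclusion criteria in Protocol section 5.2, group two is "Patient enrolled in the restrictive transfusion strategy group of ABC post ICU trial (Haemoglobin concentration at ICU discharge of >94g/L" and group three is "Patient enrolled in the liberal transfusion strategy group of the ABC post ICU study (Haemoglobin concentration at ICU discharge of >94g/L". Both limits sit in a parenthesis after the requirement to be an ABC participant.

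Other sections describe the same patients differently:

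- Section 2 lists the ABC entry criterion as "Hb≤94g/L when ready for ICU discharge or during the first seven days following the decision by the treating clinician" that the patient is fit to leave the ICU.
- Section 4.1 titles the groups "Anaemic ICU survivors - usual care (restrictive) transfusion strategy" and "Anaemic ICU survivors - liberal transfusion strategy". It defines them by ABC consent and allocation and sets no haemoglobin limit.
- Section 3 describes the ventilated comparison cohort outside ABC as patients who "were not eligible for the ABC post ICU study due to lack of anaemia". Section 5.2 gives that cohort, group one, no haemoglobin limit.
- Section 10.1 bases the target for groups two and three on ABC recruitment at the site and an assumed uptake, with no allowance for haemoglobin exclusions.
- Section 5.1 allows extra recruitment to the other groups, up to 40 in total, if one group is slow.

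**The concern.** The same number, 94 g/L, appears with opposite inequalities for the same people. The wrong or misplaced one is in the section that screening staff apply and auditors check. Groups two and three are the only randomised cohorts and make up 20 of the 40 planned participants. Comparing them on exercise capacity and fatigue is the stated purpose of the sub-study at the end of section 2.

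If the parenthesis is applied as a filter, it removes the patients those groups are meant to contain and keeps those who were least anaemic on leaving the ICU. If staff set it aside and recruit on ABC enrolment alone, each patient at or below 94 g/L at discharge is enrolled against a written inclusion criterion, and section 13.4 says that prospective waivers will not be approved.

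**Working it through.** **Step 1. The two rules side by side.**

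| Haemoglobin course | ABC entry (section 2) | Section 5.2, groups two and three |
|---|---|---|
| ≤94 g/L at ICU discharge | met | not met |
| >94 g/L at discharge, ≤94 g/L within seven days | met | met |
| >94 g/L at discharge and throughout the seven days | not met | fails, because not in ABC |

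Only the middle row satisfies both. The table treats the value when ready for discharge (section 2) and the value at discharge (section 5.2) as the same measurement. The protocol does not say how they might differ.

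**Step 2. Reproduce the plan's target.** The inputs are all from section 10.1. It states: "The estimated recruitment to the ABC post-ICU trial at the Edinburgh Royal Infirmary is 2 patients per month". It also gives at least 18 months of recruitment, 35 to 40 ABC patients expected, about 50% uptake, and a target of 20 (10 per arm).

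- ABC patients: 2 × 18 = 36, inside the stated 35 to 40.
- Recruits = ABC patients × uptake: 35 × 0.5 = 17.5; 36 × 0.5 = 18; 40 × 0.5 = 20.

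The target of 20 is reached at the top of the range, and only if every ABC patient is eligible on haemoglobin.

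**Step 3. Apply section 5.2 as written.** Let f be the share of ABC patients at the site whose ICU-discharge haemoglobin was above 94 g/L. Expected recruits = ABC patients × 0.5 × f = f × (17.5 to 20). The protocol does not give f, so the values below are assumptions.

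| Assumed f | Expected recruits, groups two and three together |
|---|---|
| 0% | 0 |
| 5% | 0.9 to 1.0 |
| 10% | 1.8 to 2.0 |
| 20% | 3.5 to 4.0 |
| 30% | 5.3 to 6.0 |
| 50% | 8.8 to 10.0 |

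Reaching 20 from 40 ABC patients needs f = 20 / (40 × 0.5) = 100%.

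**Step 4. Is the sign a reading error or a deliberate restriction?** The sign is the same in two separate criteria, and the ≤ sign is intact in section 2, so a fault in text extraction is unlikely. The eligibility changes in the amendment table include no haemoglobin limit. The group titles in section 4.1 and the recruitment arithmetic in section 10.1 are both at odds with a lower limit above 94 g/L.

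**The case against.** The strongest reply is that ABC enrolment is the operative criterion and the parenthesis is only a mis-signed description of the ABC population. Section 4.1 defines the groups by ABC allocation alone, section 5.4 expects co-enrolment with ABC, and section 10.1 counts all ABC patients. On that reading staff would recruit any consenting ABC participant who met the other criteria, and no one would be lost on haemoglobin. This is plausible, and the protocol does not establish that the parenthesis was applied as a separate screen. It does not rescue the text: as a description it still contradicts section 2, and it stands among the inclusion criteria.

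Two further points stand. This is an exploratory feasibility study with no power claim, its feasibility endpoints in section 3.2.1 are not between-arm comparisons, and the section 5.1 top-up protects the total of 40. The top-up does not protect the randomised comparison, and reaching the total could mask its loss. Secondly, a value above 94 g/L is what one might expect of the non-anaemic cohort in section 3, so the parenthesis may be misplaced rather than reversed. The text does not settle this, and simply deleting the parenthesis could remove the only trace of an intended group one criterion.

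A reader might also infer that nearly all ABC patients are excluded, that the comparison shrinks towards none against none, or that every enrolled patient becomes an eligibility deviation. The documents support none of these. The first two depend on f, which is not given. The third is wrong for any patient who meets both rules.

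**Conclusion.** The point holds as an internal contradiction in the operative eligibility section, probably clerical; nothing suggests that anyone chose to exclude anaemic patients from groups titled as anaemic. The firm statement is that, read literally, section 5.2 excludes every patient who entered ABC on an ICU-discharge haemoglobin of 94 g/L or below.

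The size of the loss is conditional. It rests on a literal reading, on the recruitment and uptake figures in section 10.1, and on an assumed f. Across f from 0 to 50%, the groups planned at 20 would yield between 0 and 10 patients. If the parenthesis is treated as a faulty description and ignored, no patients are lost, but the criterion still needs correcting.

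**What to change.** In section 5.2, replace the parenthesis for groups two and three with a cross-reference to the ABC haemoglobin entry criterion in section 2, and check that the screening form applies the same rule. At the same time reconcile sections 2, 3, 4.1 and 5.2, and state whether the >94 g/L text was meant for the non-anaemic ventilated cohort that section 3 describes. If it was, write it under group one; if not, make the description in section 3 agree with the group one criteria. If patients have already been enrolled, list their ICU-discharge haemoglobin against both rules so that it is clear which were affected.

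The cost is a short protocol correction, submitted as an amendment under section 13.3, and a check of the screening form. It needs no extra patients and no change to the analysis.
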